2 LIST OF ABBREVIATIONS

Abbreviation or Specialist Term	Explanation
AE	adverse event
AESI	adverse event of special interest
ANCOVA	analysis of covariance
ATC	anatomical therapeutic chemical
AUC	area under the concentration-time curve
AUC _∞	area under the concentration-time curve from time zero to infinity
BMI	body mass index
bpm	beats per minute
C _{max}	maximum (peak) plasma concentration
CS	clinically significant
C _{ss}	steady-state drug concentration in the plasma during oral intake
C _{avg}	steady-state drug concentration in the plasma
CV	coefficient of variation
DSMB	Data Safety Monitoring Board
ECG	electrocardiogram
eCRF	electronic case report form
ET	early termination
FCS	fully conditional specification
GEE	Generalized Estimating Equation
HCG	human chorionic gonadotropin
HCRU	healthcare resource utilization
IV	intravenous
kg	kilogram
m	meter
Max	maximum
MedDRA	Medical Dictionary for Regulatory Activities
Min	minimum
mmHg	millimeter of mercury
MMRM	mixed effects model for reported measures
msec	millisecond
n	number
NCS	not clinically significant
PCS	potentially clinically significant
PCSC	potentially clinically significant change

Statistical Analysis Plan (Methods)
Study 547-PPD-304Sage Therapeutics, Inc.
CONFIDENTIAL

PHQ-9	Patient Health Questionnaire
PK	pharmacokinetic(s)
PPD	postpartum depression
PT	preferred term
QTcF	QT corrected with Fridericia's formula
SAE	serious adverse event
SAP	statistical analysis plan
SD	standard deviation
[REDACTED]	[REDACTED]
SI	International System of Units
SOC	system organ class
ss	steady state
TEAE	treatment-emergent adverse event
Tmax	time at maximum (peak) plasma concentration
WHO	World Health Organization
WHO-DDE	World Health Organization-Drug Dictionary Enhanced

3 INTRODUCTION

This Statistical Analysis Plan (SAP) is based on the approved clinical study protocol Version 4.0 dated 20 December 2019.

The purpose of the SAP is to describe in detail the statistical methodology and the statistical analyses to be conducted for data presentation for Study 547-PPD-304, a multicenter, open-label study evaluating doses up to 90 mcg/kg/h of brexanolone in adolescent female subjects with postpartum depression.

All patients who received the active study treatment brexanolone will be presented, which includes patients who were randomized in the earlier versions of the protocol (Protocol Version 1.0, dated 23 January 2018, Version 2.0, dated 11 September, 2018, and Version 3.0 dated 03 June 2019), and received the active study treatment, as well as the patients who are enrolled under Protocol Version 4.0, the open-label study.

In addition, for the patients enrolled under the double blinded protocol versions (Protocol Version 1.0, dated 23 January 2018, Version 2.0, dated 11 September, 2018, and Version 3.0 dated 03 June 2019), all of their data will be presented according to their randomized treatment arms (placebo and brexanolone).

All analyses and summary outputs will be generated using SAS® version 9.4 (or higher).

4 STUDY OBJECTIVES

4.1 Primary Objective

- To evaluate the safety and tolerability of brexanolone when administered to adolescent female subjects diagnosed with postpartum depression (PPD).

4.2 Secondary Objectives

- To assess the plasma pharmacokinetic (PK) profile of brexanolone and, when appropriate, metabolites of brexanolone

5 STUDY ENDPOINTS

5.1 Primary Endpoint

- Incidence of treatment-emergent adverse events (TEAEs)

5.2 Secondary Endpoints

- PK parameters derived from plasma concentrations of brexanolone and, when appropriate, metabolites of brexanolone

Statistical Analysis Plan (Methods)

Study 547-PPD-304

Sage Therapeutics, Inc.
CONFIDENTIAL

- Mean changes from baseline in clinical laboratory measures, vital signs, electrocardiogram (ECG) and concomitant medication use.

6 STUDY DESIGN

6.1 Overall Design

In previous Versions 1 through 3 of this protocol, subjects were randomly assigned to active or placebo study drug in a blinded manner. With the current Amendment 3/Version 4, the study has been converted to an open-label study where all subjects will receive brexanolone.

This is a Phase 3, open-label study designed to evaluate the safety, tolerability, and PK of brexanolone in adolescent female subjects diagnosed (by Structured Clinical Interview for DSM-5 Axis I Disorders [SCID-5]) with PPD. Subjects will be administered a single, 60-hour continuous IV infusion of brexanolone. Each subject's involvement is up to 47 days, including a maximum 14-day Screening Period (from Day -14 through day -1, inclusive), a 3-day (60 hours of treatment and an additional 12 hours for completion of 72-hour assessments), and a Follow-up Period through Day 30 (\pm 3 days).

In Study 547-PPD-304, once subjects are confirmed as eligible for the study, subjects will be administered brexanolone. On the morning of dosing (Day 1), subjects will begin a 4-hour dose titration period of 30 mcg/kg/hour (0-4 hours), then 60 mcg/kg/hour (4-24 hours), then

Statistical Analysis Plan (Methods)
Study 547-PPD-304

Sage Therapeutics, Inc.
CONFIDENTIAL

90 mcg/kg/hour (24-52 hours); followed by a decrease to 60 mcg/kg/hour (52-56 hours), and 30 mcg/kg/hour (56-60 hours) as shown in [Table 1](#).

Table 1: Infusion Rates for 547-PPD-304

Time point	Infusion Rate (mcg/kg/hour)				
	Day 1 0-4 hours	Day 1 4-24 hours	Day 2-3 24-52 hours	Day 3 52-56 hours	Day 3 56-60 hours
Dose(mcg)	30	60	90	60	30

Total brexanolone dosing will occur over 60 hours.

The end of the Treatment Period coincides with the beginning of the Follow-up Period. Follow-up visits will be conducted on Day 7, Day 14, Day 21, Day 30.

6.2 Sample Size and Power

No formal sample size calculation was made for this study. The planned sample size of 20 adolescent subjects treated with brexanolone should be appropriate to characterize the PK and safety profile.

The planned sample size of 20 includes those subjects who received brexanolone as blinded study drug during earlier versions of the protocol when the study was a randomized, double-blind, placebo-controlled study.

6.3 Randomization and blinding

In this open-label study, all subjects will be administered a single, continuous, 60-hour intravenous (IV) infusion of brexanolone starting on Day 1.

This study was previously conducted (in Protocol Versions 1 through 3) as a randomized placebo-controlled double-blind study. An independent (DSMB) will have access to all safety data as necessary.

7 MODIFICATIONS

7.1 Modifications from the Approved Clinical Study Protocol

Not applicable.

7.2 Modifications from the Approved Statistical Analysis Plan

Not applicable.

7.3 Modifications from the Approved DSMB Charter

DSMB Charter 1.0, dated 31 Oct 2018, specified periodic data review meetings to be scheduled quarterly after the first meeting.

Statistical Analysis Plan (Methods)
Study 547-PPD-304

Sage Therapeutics, Inc.
CONFIDENTIAL

DSMB Charter 2.0, dated 16 July 2019, updated the periodic data review meetings scheduled quarterly or when a minimum of five (5) new subjects are enrolled and 14-day visit data are available.

BREXANOLONE DSMB Charter Version 1.0, dated 20 October 2020, a brexanolone program-wide DMC charter has been created to cover all ongoing brexanolone studies: 547-PPD-304 and 547-ARD-301.

8 ANALYSIS SETS

8.1 All Subjects Set

The All Subjects Set will include every subject who has given written informed consent. This set will be used for subject disposition.

8.2 Randomized/enrolled Set

The Randomized/enrolled Set will include subjects who have been randomized in earlier double blinded versions of the protocol and subjects who are enrolled in the current open-label version of the protocol. Subjects will be classified according to randomized treatment for the double-blinded treatment and also for the active study treatment brexanolone they receive.

8.3 Safety Set

The Safety Set will include all randomized/enrolled subjects who start the infusion of study drug. Subjects will be classified according to actual treatment received. This analysis set will be used for subject demographics and baseline characteristic summaries and all safety analyses.

8.4 Efficacy Set

The Efficacy Set will include the subset of the Safety Set who have a valid baseline efficacy assessment and at least one post-baseline efficacy assessment.

8.5 Pharmacokinetics Set

The PK Set will include all subjects in the Safety Set who have at least one evaluable post-baseline PK sample. Subjects will be classified according to actual treatment received. This analysis set will be used for all PK analyses.

9 STATISTICAL ANALYSIS

9.1 General Considerations

Unless otherwise specified, continuous endpoints will be summarized with number (n), mean, standard deviation (SD), median, minimum (min) and maximum (max). The minimum and maximum will be reported with the same degree of precision (ie, the same number of decimal places) as the raw data. Measures of location (mean and median) will be reported to 1 degree of precision more than the raw data. Measures of spread (SD) will be reported to 2 degrees of precision more than the raw data. In addition, change from baseline values will be calculated at each time point and summarized descriptively. For categorical

Statistical Analysis Plan (Methods)
Study 547-PPD-304Sage Therapeutics, Inc.
CONFIDENTIAL

endpoints, descriptive summaries will include counts and percentages. Percentages will be presented to 1 decimal place except for 0%, which will be presented as “0”, and 100%, which will be presented as “100”.

All analyses and summary outputs will be generated using SAS® version 9.4 (or higher).

All subject data, including those derived, will be presented in the subject data listings. The listings will display all subjects who were enrolled. In general, the subject data listings will be sorted by randomized treatment group, subject number and assessment visit and date (and time, if applicable). The summary tables will be presented descriptively by treatment group.

9.1.1 Study Day Definition

Study day is defined as follows:

- The day when the study drug infusion is started is designated as Day 1.
- For visit days after Day 1, study day = visit date – Day 1 date + 1.
- For visit days prior to Day 1, study day = visit date – Day 1 date. Thus, study days for the screening visit are negative numbers. There is no “Day 0”.

9.1.2 Baseline Definition

For the purpose of all safety and efficacy analyses where applicable, baseline is defined as the last non-missing measurement prior to the start of study drug administration.

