9.3.3 Visit Windows

The unscheduled or early termination (ET) visit will be mapped to a scheduled visit for analysis using the date/time of collection/assessment as a basis to determine study day/hour and then study day/hour will be mapped to the intended visit. Once analysis visit windows get assigned, all visits, including scheduled visits, unscheduled visits, and ET visits will be eligible for being flagged as the “analyzed record” within the analysis window. A subject’s individual analysis visit window could potentially contain more than 1 visit. In the event of multiple visits falling within an analysis window or in case of a tie, the following rules will be used in sequence to determine the “analyzed record” for the analysis visit window:

- If there is a scheduled visit/day for the analysis visit window, then the scheduled visit/day data will be used.
- If there is no scheduled visit/day for the analysis visit window, the data closest to the scheduled study day/hour will be used.
- If there is no scheduled visit/day for the analysis visit window and there are visits equally close to the day/hour of scheduled visit, the latest data will be used.

[figure not shown]
The data not flagged as the “analyzed record” will also be listed in subject listings.

The Follow-up Period in this version of the protocol was reduced from Day 90 ± 7 days to Day 30 ± 3 days for consistency with the Follow-up Period in the adult PPD studies for brexanolone.

Statistical Analysis Plan (Methods)
Study 547-PPD-304

Sage Therapeutics, Inc.
CONFIDENTIAL

Tables 4 – 8 summarize the visit window for all the efficacy endpoint under both follow up schedules.

[figure not shown]
Statistical Analysis Plan (Methods)
Study 547-PPD-304

Sage Therapeutics, Inc.
CONFIDENTIAL

Statistical Analysis Plan (Methods)
Study 547-PPD-304

Sage Therapeutics, Inc.
CONFIDENTIAL

Statistical Analysis Plan (Methods)
Study 547-PPD-304

Sage Therapeutics, Inc.
CONFIDENTIAL

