9.4.4 Clinical Laboratory

9.4.4.1 Hematology, Serum Chemistry, Coagulation

Blood samples will be collected for coagulation at screening, and hematology and serum chemistry, throughout the study. Analytes to be evaluated are summarized in [Table 15](#).

All blood samples will be sent to the central laboratory. Subjects may be considered eligible for the study based on results reported by a local laboratory; however, screening samples must also be sent to the central laboratory. Both local and central screening laboratories must adhere to the visit window provided in [Appendix A](#).

Table 15: Summary of Laboratory Analytes

Hematology	Complete blood count (red blood cells, white blood cells with differentiation and absolute values, hemoglobin, hematocrit, reticulocytes, and platelets)
------------	--

Statistical Analysis Plan (Methods)
Study 547-PPD-304Sage Therapeutics, Inc.
CONFIDENTIAL

Coagulation (at Screening only)	Activated partial thromboplastin time, prothrombin time, and international normalized ratio
Biochemistry	Serum electrolytes (sodium, potassium, chloride, bicarbonate or total carbon dioxide, calcium, and phosphorus) renal function tests (creatinine and blood urea nitrogen); liver function tests (total bilirubin, alkaline phosphatase, aspartate aminotransferase, alanine aminotransferase, and gamma glutamyl transferase); thyroid stimulating hormone; total protein; albumin and glucose (fasting or non-fasting)

All clinical laboratory test results outside the reference range will be interpreted by the Investigator as abnormal, not clinically significant; or abnormal, clinically significant (CS). Screening results considered abnormal and CS at the Screening Visit may make the subject ineligible for the study pending review by the Investigator or Medical Monitor. Clinically significant abnormal results after screening will be considered and reported as AEs.

Summary tables will include descriptive statistics for the actual values and changes from baseline by scheduled time point in hematology, serum chemistry, and coagulation by treatment group. Frequency counts and percentages will be presented over time for these categorical data by treatment.

Shift analysis pre- and post-treatment will be presented for the following laboratory categories (low, normal and high).

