Number and percent of subjects with liver injury as defined by Hy's law will be presented. Hy's law is defined as ALT or AST > 3 times of upper limit of normal; and total bilirubin > 2 times of upper limit of normal, and alkaline phosphatase < 2 time of upper limit of normal.

All parameters will be converted to consistent units according to the International System of Units (SI) before summarization.

All clinical laboratory results will be listed by subject and timing of collection. Out-of-range values will be flagged as low, high, or abnormal, where applicable.

The number and percentage of subjects with potentially clinically significant (PCS) values at any time after study drug infusion will be summarized by treatment group for the hematology and chemistry parameters defined in [Table 16](#) and [Table 17](#). PCS laboratory values will also be listed by subject.

Statistical Analysis Plan (Methods)
Study 547-PPD-304Sage Therapeutics, Inc.
CONFIDENTIAL**Table 16: Hematology Potentially Clinically Significant Values**

Laboratory Parameter	Sex	Units	Criteria for PCS Values (Observed values)	
			High	Low
Hemoglobin	Male	g/L	>185	<115
	Female	g/L	>170	<100
Hematocrit	Male	Fraction of 1	>0.55	<0.385
	Female	Fraction of 1	>0.49	<0.345
Platelet count		10 ⁹ /L	>600	<125
White blood cell		10 ⁹ /L	>15	<2.5
Basophils		10 ⁹ /L	>0.5	NA
Eosinophils		10 ⁹ /L	>1.5	NA
Neutrophils		10 ⁹ /L	NA	<1.5
Lymphocytes		10 ⁹ /L	>6.0	<0.5
Monocytes		10 ⁹ /L	>1.4	NA

Abbreviations: PCS = Potentially Clinically Significant

Statistical Analysis Plan (Methods)
Study 547-PPD-304Sage Therapeutics, Inc.
CONFIDENTIAL**Table 17: Chemistry Potentially Clinically Significant Values**

Laboratory Parameter	Units	Criteria for PCS Values (Observed values)	
		High	Low
Albumin	g/L	>70	<28
Blood urea nitrogen	mmol/L	>10.71	NA
Calcium	mmol/L	>2.75	<2.0
Chloride	mmol/L	>120	<90
Creatinine	mmol/L	>3xULN or >3x Baseline	
Gamma Glutamyl Transferase		>3xULN	
Glucose	mmol/L	>13.9	<2.8
Sodium	mmol/L	>150	<132
Potassium	mmol/L	>5.4	<3.3
Protein	g/L		<45
Bicarbonate	mmol/L	>34	<18
Chloride	mmol/L	>120	<90
Phosphorus	mmol/L	>1.94	<0.61
Liver Function Tests (LFT)			
Bilirubin	µmol/L	>2xULN	NA
Aspartate Aminotransferase	U/L	>3xULN	NA
Alanine Aminotransferase	U/L	>3xULN	NA
Alkaline Phosphatase	U/L	>1.5xULN	NA

Abbreviations: PCS = Potentially Clinically Significant

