9.4.5 Electrocardiogram

A baseline 12-lead ECG will be performed during screening. The following ECG parameters will be recorded: heart rate (bpm), pulse rate (PR) (msec), QRS (msec), QT (msec), and QT corrected with Fridericia's formula (QTcF) (msec).

QTcF (msec) is calculated as: QT (msec) / $RR^{1/3}$, where $RR = 60 / \text{heart rate (bpm)}$.

All ECG results will be interpreted by the Investigator as 'normal' 'abnormal, NCS'; or 'abnormal, CS'. If 'abnormal', details will be provided.

The actual value at each time point and change from baseline at each post-baseline time point will be summarized by treatment group. The number and percentage of subjects with 'normal', 'abnormal, not clinically significant' and 'abnormal, clinically significant' ECG results will be summarized at baseline and each post-baseline time point.

All ECG data will be listed by subject and time of measurement. Mean values of ECG parameters over time will be presented graphically by treatment group.

Additionally, the number and percentage of subjects with PCS and potentially clinically significant change (PCSC) values will be summarized for such occurrence any time post-baseline. Potentially clinically significant values will be identified for ECG parameters as outlined in the following table. This analysis includes triplicate values individually and is not based on average value. In addition, any PCS value at any time post-baseline will be summarized as shown in [Table 18](#).

Table 18: ECG Potentially Clinically Significant Values

ECG	Units	Criteria for PCS Values (Observed values)		Criteria for PCSC values (Change from Baseline)	
		High	Low	Increase	Decrease
QTcF Interval	msec	>450 but \leq 480 >480 but \leq 500 >500	NA	\geq 30 to 60 >60	NA

Abbreviations: PCS = Potentially Clinically Significant; PCSC = Potentially Clinically Significant Change; NA=Not Available

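### The Table 11 lab baseline window opens at D-7, but the only scheduled pre-dose lab draw may fall from D-14, and the SAP does not say whether Table 11 or Section 9.1.2 governs

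*SAP*

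**What the plan says.** Section 9.1.2 gives one baseline rule for all safety and efficacy analyses, where applicable: "baseline is defined as the last non-missing measurement prior to the start of study drug administration". It does not limit how far back that measurement may lie.

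Section 9.4.1, Table 11, sets the analysis windows for hematology and serum chemistry. Its Baseline row has an expected day of D-1 and a window of D-7 to D1H0. Section 9.4.1 adopts the mapping and flagging rules of Section 9.3.3, which include: "Once analysis visit windows get assigned, all visits, including scheduled visits, unscheduled visits, and ET visits will be eligible for being flagged" as the record to be analyzed.

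Section 6.1 allows a screening period of up to 14 days, D-14 to D-1. In Appendix A the clinical laboratory row has one mark before dosing, in that screening column, and none at Day 1 Hour 0. Section 9.4.4.1 holds screening samples to the same schedule: "Both local and central screening laboratories must adhere to the visit window provided in" Appendix A.

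Baseline is then used in several places. Section 5.2 lists as a secondary endpoint "Mean changes from baseline in clinical laboratory measures, vital signs, electrocardiogram (ECG) and concomitant medication use". Section 9.4.4.1 states: "Summary tables will include descriptive statistics for the actual values and changes from baseline by scheduled time point in hematology", and the same for the other laboratory panels. It also plans shift tables, and Table 17 sets the creatinine limit at ">3xULN or >3x Baseline".

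**The concern.** The baseline window for laboratory data is half as long as the period in which the only planned pre-dose sample may be taken. A sample drawn on D-14 to D-8 complies with the schedule and meets the definition in 9.1.2, but Table 11 has nowhere to put it. Two programmers could follow this SAP faithfully and produce different laboratory tables.

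If Table 11 is applied as written, a subject with an early draw has no baseline for change scores, shift tables or the baseline limb of the creatinine criterion. Section 9.1.3 rules out imputation of safety data, so the gap stays. A mixed reading also fails: if change scores use 9.1.2 while the Baseline row of actual values uses Table 11, the baseline n and the change-score n can disagree within one table.

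There are two smaller inconsistencies of the same kind. The Screening rows of Tables 12 and 13 also start at D-7. Section 9.4.5 says "A baseline 12-lead ECG will be performed during screening", whereas Table 12 places the ECG baseline at D1H0. ECG and vital signs both have a scheduled Hour 0 assessment, so no loss of baseline is claimed for them.

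**Working it through.** **Inputs from the SAP**
- Screening period: D-14 to D-1 (Section 6.1, Appendix A)
- Day numbering: no Day 0 (Section 9.1.1)
- Laboratory Baseline window: D-7 to D1H0 (Table 11)
- Pre-dose laboratory draws: one, at screening (Appendix A)
- Planned subjects treated with brexanolone: 20 (Section 6.2)

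**Check of the SAP's own figure.** D-14 to D-1 is 14 days. Follow-up to Day 30 plus 3 days ends on Day 33. 14 + 33 = 47, which agrees with the maximum of 47 days in Section 6.1. The 14-day screening period is therefore consistent within the document.

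**Overlap of the two windows**
- Permitted draw days: D-14 to D-1 = 14
- Inside Table 11: D-7 to D-1 = 7
- Outside Table 11: D-14 to D-8 = 7, and 7/14 = 50% of the permitted days

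This counts days, not subjects. The document gives no distribution of draw days.

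**Subjects without a laboratory baseline.** If 9.1.2 governs, the number is 0 of 20. If Table 11 governs, let p be the share of subjects whose draw falls before D-7 with no later pre-dose draw. p is an assumption, shown as a range. The expected loss is 20p, the chance that at least one subject is affected is 1 - (1 - p)^20, and the standard error of a mean change is multiplied by sqrt(20/n) at the same SD.

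| Assumed p | Expected loss | n left | Chance of at least one | SE multiplier |
|---|---|---|---|---|
| 10% | 2 | 18 | 0.878 | sqrt(20/18) = 1.054 (+5%) |
| 25% | 5 | 15 | 0.997 | sqrt(20/15) = 1.155 (+15%) |
| 50% | 10 | 10 | >0.999 | sqrt(20/10) = 1.414 (+41%) |

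The 50% row is what draws spread evenly over the screening period would give.

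**Search for a precedence rule.** Sections 9.1.2, 9.3.3 and 9.4.1 contain none. Sections 7.1 and 7.2 record no modifications.

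**The case against.** The strongest reply is that the SAP largely settles the matter in favour of 9.1.2. That is the only section headed as a baseline definition, and it covers all safety and efficacy analyses. Section 9.1.3 says that all subjects are to be analyzed with every available value, which fits badly with discarding an on-schedule sample because it was taken on D-8. Section 9.3.3 opens with the placement of unscheduled and early termination visits, so the windows can be read as a tool for placing visits that leaves the choice of baseline to 9.1.2. This is the better reading, but the text does not compel it. Section 9.1.2 applies only where applicable, 9.3.3 puts scheduled visits through the windows too, and Table 11 is the more specific rule and names its row Baseline.

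The second reply concerns size, and much of it stands. The loss counts require three things together: Table 11 governs, the draw is early, and there is no later pre-dose draw. The 20 subjects include some treated under protocol Versions 1 to 3, whose laboratory schedule is not shown. Laboratory summaries are descriptive, and Section 9.1 does not list a standard error among the statistics, so the multipliers only illustrate lost precision.

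The third reply, that the consequence is narrow, is also right. TEAE incidence, post-dose actual values, Hy's law counts, the liver thresholds and every limit in Tables 16 and 17 except one limb for creatinine need no baseline. All laboratory results are listed by subject, so an early screening value remains visible.

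**Conclusion.** The concern holds. The Table 11 Baseline window does not cover 7 of the 14 days on which the only scheduled pre-dose laboratory sample may be drawn. It conflicts with 9.1.2 for those days, and nothing in the SAP says which rule wins. Applied as written, Table 11 would discard valid baselines for a stated secondary endpoint.

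The number of subjects affected is unknown. It is 0 of 20 if 9.1.2 governs. It is 2, 5 or 10 of 20 if Table 11 governs under the assumed shares of 10%, 25% or 50%. The finding that Appendix A has no Hour 0 laboratory draw rests on a table whose layout is broken in the text version. However, the neighbouring rows for drug and alcohol tests, pregnancy test, vital signs and ECG each show a second pre-dose mark that the laboratory row lacks.

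This should be corrected. The primary endpoint is not affected.

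**What to change.** 1. In Table 11, change the Baseline window to the last non-missing value from D-14 up to the start of infusion.
2. Add one sentence to Section 9.4.1: *Baseline for all safety parameters follows Section 9.1.2; the windows do not restrict it.* This is the essential step. It also ensures that the D-14 bound in Table 11 does not become a new look-back limit.
3. For consistency only, start the Screening rows of Tables 12 and 13 at D-14, and reword the first sentence of Section 9.4.5 so that the ECG baseline follows 9.1.2.

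The cost is three table cells and two sentences, with no new data and no change to study conduct.
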